8.2.2 Reporting

Every SAE, regardless of suspected causality, occurring after the patient has provided informed consent and until 30 days after the patient has stopped study treatment/participation must be reported to Novartis within 24 hours of learning of its occurrence.

Any SAE experienced after this 30-day period should only be reported to Novartis if the investigator suspects a causal relationship to the study drug.

Recurrent episodes, complications, or progression of the initial SAE must be reported as follow-up to the original episode within 24 hours of the investigator receiving the follow-up information. An SAE occurring at a different time interval or otherwise considered completely unrelated to a previously reported one should be reported separately as a new event.

Information about all SAEs is collected and recorded on the Serious Adverse Event Report Form; all applicable sections of the form must be completed in order to provide a clinically thorough report. The investigator must assess and record the relationship of each SAE to each specific study drug, complete the SAE Report Form in English, and send the completed, signed form by fax within 24 hours to the oncology Novartis Drug Safety and Epidemiology (DS&E) department.

The telephone and telefax number of the contact persons in the local department of Drug Safety and Epidemiology (DS&E), specific to the site, are listed in the investigator folder provided to each site. The original copy of the SAE Report Form and the fax confirmation sheet must be kept with the case report form documentation at the study site.

Follow-up information is sent to the same contact(s) to whom the original SAE Report Form was sent, using a new SAE Report Form stating that this is a follow-up to the previously reported SAE and giving the date of the original report. Each re-occurrence, complication, or progression of the original event should be reported as a follow-up to that event regardless of when it occurs. The follow-up information should describe whether the event has resolved or continues, if and how it was treated, and whether the patient continued the study or withdrew from study participation.

If the SAE is not previously documented in the Investigator's Brochure or Package Insert (new occurrence) and is thought to be related to the Novartis study drug, an oncology Novartis Drug Safety and Epidemiology (DS&E) department associate may urgently require further information from the investigator for Health Authority reporting. Novartis may need to issue an Investigator Notification (IN), to inform all investigators involved in any study with the same drug that this SAE has been reported. Suspected Unexpected Serious Adverse Reactions (SUSARs) will be collected and reported to the competent authorities and relevant ethics committees in accordance with European Directive 2001/20/EC or as per national regulatory requirements in participating countries.

8.3 Emergency unblinding of treatment assignment

Not applicable, this is an open label study.

8.4 Pregnancies

Not applicable; this study will enroll post-menopausal women only.

8.5 Warnings and precautions

No evidence available at the time of the approval of this study protocol indicated that special warnings or precautions were appropriate, other than those noted in the provided [Investigator Brochure]. Additional safety information collected between IB updates will be communicated in the form of Investigator Notifications. This information will be included in the patient informed consent and should be discussed with the patient during the study as needed.

9 Data collection and management

[figure not shown]
9.1 Data confidentiality

Information about study subjects will be kept confidential and managed under the applicable laws and regulations. Those regulations require a signed subject authorization informing the subject of the following:

- What protected health information (PHI) will be collected from subjects in this study
- Who will have access to that information and why
- Who will use or disclose that information
- The rights of a research subject to revoke their authorization for use of their PHI.

In the event that a subject revokes authorization to collect or use PHI, the investigator, by regulation, retains the ability to use all information collected prior to the revocation of subject authorization. For subjects that have revoked authorization to collect or use PHI, attempts should be made to obtain permission to collect follow-up safety information (e.g. has the subject experienced any new or worsened AEs) at the end of their scheduled study period.

The data collection system for this study uses built-in security features to encrypt all data for transmission in both directions, preventing unauthorized access to confidential participant information. Access to the system will be controlled by a sequence of individually assigned user identification codes and passwords, made available only to authorized personnel who have completed prerequisite training.

9.2 Site monitoring

Before study initiation, Novartis personnel (or designated CRO) will review the protocol and CRFs with the investigators and their staff at a site initiation visit. During the study, the field monitor will visit the site regularly to check the completeness of patient records, the accuracy of entries on the eCRFs, the adherence to the protocol and to Good Clinical Practice, the progress of enrolment, and to ensure that study drug is being stored, dispensed, and accounted for according to specifications. Key study personnel must be available to assist the field monitor during these visits.

The investigator must maintain source documents for each patient in the study, consisting of case and visit notes (hospital or clinic medical records) containing demographic and medical information, laboratory data, electrocardiograms, and the results of any other tests or assessments. All information on eCRFs must be traceable to these source documents in the patient's file. The investigator must also keep the original informed consent form signed by the patient (a signed copy is given to the patient).

The investigator must give the monitor access to all relevant source documents to confirm their consistency with the eCRF entries. Novartis monitoring standards require full verification for the presence of informed consent, adherence to the inclusion/exclusion criteria, and documentation of SAEs. Additional checks of the consistency of the source data with the eCRFs are performed according to the study-specific monitoring plan.

9.3 Data collection

Novartis will supply the investigator site with an Electronic Data Capture (EDC) system that has been fully validated and conforms to 21 CFR Part 11 requirements.

Novartis (or designated CRO) will train designated investigator site staff on the EDC system. Investigator site staff will not be given access to the EDC system until they have been trained.

The investigator will notify Novartis and the CRO of any changes in study personnel responsible for entering study related data into the EDC system. Once notified, Novartis (or designated CRO) will ensure that the new site personnel are adequately trained, understand the study protocol requirements and can properly use the EDC system.

Designated investigator staff will enter the data required by the protocol into the eCRFs through the EDC system. Automatic validation programs check for data discrepancies in the eCRFs and, by generating appropriate error messages, allow modification or verification of the entered data by the investigator staff before transfer to Novartis via a secure Virtual Private Network. If applicable, the investigator must certify that the data are complete and accurate by signing a memo prior to database lock.

The principal investigator is responsible for assuring that the data entered into the eCRF is complete, accurate, and that entries and updates are performed in a timely manner.

After database lock, the investigator will receive a CD-ROM or paper copies of the patient data for archiving at the investigational site.

9.4 Database management and quality control

Data recorded on the eCRFs will be reviewed by a designated CRO staff for completeness and accuracy following their own internal standard operating procedures that have been reviewed and approved by Novartis.

Site personnel will be instructed to make any required corrections or additions. Obvious errors are corrected by CRO Data Management staff. Queries are sent to the investigational site using an electronic data query system. The designated investigator site staff is required to respond to the query and make any necessary changes to the data within a reasonable timeframe. If the electronic query system is not used, a paper Data Query Form will be faxed to the site. Site personnel will complete and sign the faxed copy. This copy will then be faxed back to the CRO Data Management staff that will make the correction to the database. The signed copy of the Data Query Form is kept at the investigator site.

Concomitant medications entered into the database will be coded using the WHO Drug Reference List, which employs the Anatomical Therapeutic Chemical classification system. Medical history/current medical conditions and adverse events will be coded using the Medical dictionary for regulatory activities (MedDRA) terminology.

Samples and/or data may be processed centrally and the results will be sent electronically to Novartis (or a designated CRO).

At the conclusion of the study, the occurrence of any emergency code breaks will be determined after return of all code break reports and unused drug supplies to Novartis (or designated CRO). The occurrence of any protocol violations will be determined. After these actions have been completed and the database has been declared to be complete and accurate, the database will be locked and made available for data analysis. Any changes to the database after that time can only be made by joint written agreement between the Global Head of Biostatistics and Statistical Reporting and the Global Therapeutic Area Head.

[figure not shown]
10 Statistical methods and data analysis

The study is designed as an open-label, single-arm, phase IIIB trial to assess the safety, tolerability and efficacy of everolimus plus exemestane in postmenopausal women with hormone receptor positive breast cancer progressing following prior therapy with non-steroidal aromatase inhibitors.

It is planned that the data from participating centers in this protocol will be combined, so that an adequate number of patients will be available for analysis. The data will be analyzed by Novartis and/or designated CRO. Any data analysis carried out independently by the investigator should be submitted to Novartis before publication or presentation.

10.1 Analysis sets

The Full Analysis Set (FAS) consists of all patients to whom treatment was assigned and who received at least one dose of study drug.

The Per-protocol Set (PP) consists of a subset of patients of the FAS who did not show major deviations from the protocol procedures that may have an impact on the study outcome. Criteria that are assumed to have such an impact will be defined in the Protocol Deviations Module of the Validation and Planning (VAP) documentation, and assessed before database lock during the blinded review meeting.

The Safety Set consists of all patients who received at least one dose of study drug and had at least one post-baseline safety assessment. The statement that a patient had no adverse events (on the Adverse Event CRF) constitutes a safety assessment. Patients who have received at least one dose of study drug but who have no post-treatment safety data of any kind would be excluded from the safety population.

10.2 General statistical methods

The data will be summarized with respect to demographic and baseline characteristics, efficacy observations and measurements, and safety observations and measurements. Primary efficacy and safety/tolerability analysis will be conducted at 15 months of median follow up time, i.e. at approximately two times the median PFS reported in the BOLERO-2 study (Baselga et al. 2012; Yardley D. et al. 2014). Categorical variables will be summarized by absolute and relative frequencies. Continuous variables will be summarized by descriptive statistics (number of valid and missing observations, mean, standard deviation, median, minimum, and maximum).

Time to event data including rates of affected patients will be assessed using the Kaplan-Meier method. Two-sided 95% confidence intervals will be provided for the main statistical estimators.

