As of June 30th 2014, 198 patients have been enrolled into the study.

At this stage we deem appropriate to change the end of study “until everolimus is locally reimbursed or commercialized for this indication or until all patients have been discontinued from investigational treatment due to disease progression, unacceptable toxicity, death, consent withdrawal or any other reason”, in order to:

- Facilitate treatment continuation at the single patient level in all participating countries
- Continue data collection and further strengthen the final safety and efficacy data set

The statistical plan was revised accordingly to take into account prolonged study duration and to ensure data will be analyzed will be mature enough to derive conclusive results. with primary efficacy and safety/tolerability analysis now planned at 15 months of median follow up time, i.e. at approximately two times the median PFS observed in the BOLERO-2 study.

On the other hand, as the investigational drug will be commercially available in the majority of the participating countries by the end of 2014, recruitment will end in any case in all participating countries no later than on 31st of October 2014.

Moreover, as substantial updates were included in the [Investigator’s Brochure] (version 13) recently released, relevant sessions of the protocol have been amendment accordingly, although this does not imply major changes in study implementation and conduction.

[figure not shown]
Additional minor changes were included to amend negligible inconsistencies in the previous version,

Changes to the background session:

- Updated information about everolimus clinical efficacy and safety profile have been included.

Changes to study design:

- It is specified that enrollment will end in all participating countries by the time of registration/commercial availability of everolimus in the investigational indication and in any case no later than October 31st 2014.

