- End of study has been amended to be in each participating country when everolimus is locally reimbursed or commercialized for this indication or when all patients have been discontinued from investigational treatment due to disease progression, unacceptable toxicity, death, consent withdrawal or any other reason. In those countries in which patients will be transitioned to locally reimbursed or commercialized drug supply, Novartis will have a local transition plan in order to ensure that all on-going patients will still have access to the study medication without

[figure not shown]
Changes to dose references:

- Publication from Yardley D. et al. 2014 is now included

IRB/IEC

A copy of this amended protocol must be sent to the applicable Institutional Review Board (IRBs)/Independent Ethics Committee (IECs) and Health Authorities.

The changes described in this amended protocol require IRB/IEC approval/favorable opinion and any applicable health authority authorization prior to implementation. In addition, if the changes herein affect the Informed Consent, sites are required to update and submit for approval a revised Informed Consent that takes into account the changes described in this amended protocol.

Amendment 1

Amendment rationale

As of November 18th 2013, 114 patients have been enrolled into the study.

Need for more clarity about the phase IIIb nature vs ‘expanded treatment program’ of this study has been raised in multiple occasions during discussions with Health Authorities and for internal purposes.

We thus deemed appropriate to bring more clarity about this aspect standardizing the relevant sessions of the protocol in line with the phase IIIb nature of this study, with the aim of confirming the safety and efficacy of everolimus plus exemestane for the treatment of HR-positive/Her-2-negative advanced breast cancer in Emerging Growth Markets.

Moreover, the management of selected adverse events will be updated and aligned across the everolimus program and with the last [Investigator’s Brochure] (version 12), specifically for the window of time permitted for temporary discontinuation of the treatment with everolimus upon the development of Grade 2 noninfectious pneumonitis (4 weeks in the original protocol, 3 weeks in the amended version).

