
Other assessments
	
 ● Time to deterioration of ECOG performance status, from baseline

Data analysis
	
Analysis populations: The Full Analysis Set (FAS) consists of all patients to whom treatment was assigned and who received at least one dose of study drug.
 
The Per-protocol Set (PP) consists of a subset of patients of the FAS who did not show major deviations from the protocol procedures that may have an impact on the study outcome.
 
The Safety Set consists of all patients who received at least one dose of study drug and had at least one post-baseline safety assessment. The statement that a patient had no adverse events (on the Adverse Event CRF) constitutes a safety assessment. Patients who have received at least one dose of study drug but who have no post-treatment safety data of any kind would be excluded from the safety population.
 
Sample size: The proposed sample size (up to 400 patients) is a convenience sample. The data will be summarized with respect to demographic and baseline characteristics, efficacy observations and measurements, and safety/tolerability observations and measurements. Primary efficacy and safety/tolerability analysis will be conducted at 15 months of median follow up time, i.e. at approximately two times the median PFS reported in the BOLERO-2 study .
 
Statistical methods: Demographic and other baseline characteristics will be summarized for the Full Analysis Set (FAS). Baseline characteristics include prior medication, past/current medical conditions and disease history. Concomitant medications and significant non-drug therapies prior to and after the start of the study drug will be coded according to the WHO Drug Reference List, and

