4.2 Definition of end of the study

In each participating country, the study will start after approvals are being obtained from the respective local authority and IRB and will end when everolimus is locally reimbursed or commercialized for this indication or when all patients have been discontinued from investigational treatment due to disease progression, unacceptable toxicity, death, consent withdrawal or any other reason.

In those countries in which patients will be transitioned to locally reimbursed or commercialized drug supplies, Novartis will have a local transition plan in order to ensure that all on-going patients will still have access to the study medication without any delay in their treatment.

Patients will be followed up for safety purposes for 30 days (\pm 2 days) after the last dose of study drug. At the end of the study, the progression status of all participating patients will be updated and recorded in the electronic case report form (eCRF).

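### Does the undefined 15-month median follow-up that times the primary analysis need a formal definition before the plan can be used?

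*Protocol*

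**What the plan says.** The same timing rule appears in Protocol Section 10.2 ("Primary efficacy and safety/tolerability analysis will be conducted at 15 months of median follow up time, i.e. at approximately two times the median PFS"), in the protocol summary under data analysis ("Primary efficacy and safety/tolerability analysis will be conducted at 15 months of median follow up time") and in the Amendment 2 rationale. The only explanation is that 15 months is about twice the median PFS in BOLERO-2. Amendment 2 gives the purpose: "to ensure data will be analyzed will be mature enough to derive conclusive results".

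Section 4.2 closes the study country by country: it "will end when everolimus is locally reimbursed or commercialized for this indication", or when all patients are off treatment. Amendment 2 expects that "the investigational drug will be commercially available in the majority of the participating countries by the end of 2014", and uses this to justify stopping recruitment by 31 October 2014.

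SAP Table 1.3 summarises length of follow-up in weeks, from the screening visit to the end-of-study date. It does not mention the 15-month rule. Section 10.7 says that no hypothesis will be tested.

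**The concern.** A median follow-up time needs an origin, an end point, a population and an estimator, and none is attached to the 15 months. Staggered country closure sharpens the question. If most countries close around the end of 2014 and recruitment runs to 31 October 2014, many patients could leave before 15 months. The plan does not say whether their clock stops. On one reading the cut-off falls in early 2015. On another it falls months later, or the threshold is never met.

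At stake are the date of the data cut and the ability to check that Amendment 2's maturity aim was met. The Table 1.3 median could also be mistaken for the 15-month figure.

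**Working it through.** **The plan's own figure.** Protocol Section 1.2.1.2.2 gives BOLERO-2 median PFS as 6.93 months (interim) and 7.82 months (final). Twice these is 13.86 and 15.64 months, so 15 is a fair rounding of two medians.

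**Recruitment.** Amendment 1 states "As of November 18th 2013, 114 patients have been enrolled into the study" and Amendment 2 states "As of June 30th 2014, 198 patients have been enrolled into the study". The pace is (198 − 114)/224 days = 0.375 per day. Over the 123 days from 30 June to 31 October 2014 this adds 46, so N is about 244.

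**Reading A: enrolment to a common cut-off.** Patient 122 is the median. She enters (122 − 114)/0.375 = 21 days after 18 November 2013, on about 9 December 2013. Adding 15 months gives about 10 March 2015. On 31 December 2014 she has 12.7 months.

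**Reading B: follow-up stops at closure.** Assume that a share p of patients is in countries that close on 31 December 2014, regardless of entry date. A closed-country patient can reach 15 months only if she entered by about 1 October 2013. Let *a* be the number enrolled by then. With linear accrual to 114 on 18 November 2013, *a* is 100.8 if the first patient entered on 1 October 2012 and 93.1 if on 1 March 2013. Both start dates are assumptions. The median reaches 15 months when

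p × a + (1 − p) × r = 122, so r = (122 − p × a)/(1 − p),

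where r is the enrolment rank of the patient who then has exactly 15 months at the cut-off.

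| p | r (two start dates) | 15 months reached | Later than Reading A |
|---|---|---|---|
| 0.25 | 129.1 / 131.6 | 29 Mar / 5 Apr 2015 | 0.6 / 0.9 months |
| 0.50 | 143.2 / 150.9 | 5 May / 26 May 2015 | 1.8 / 2.5 months |
| 0.75 | 185.7 / 208.7 | 27 Aug / 27 Oct 2015 | 5.6 / 7.6 months |
| 0.90 | 313 / 382 (above 244) | not reached | – |

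The threshold becomes unreachable when r exceeds 244, that is when p exceeds 122/(244 − a) = 0.85 or 0.81. Simulation with random allocation of patients to closed countries gives dates within a few days of these: 31 March to 6 April at 25%, 9 to 29 May at 50%, and 1 September to 31 October at 75%. At 90%, 98% to 100% of runs never reach 15 months.

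**What the documents already settle.**
- Origin: PFS starts at treatment start (Section 10.6.1.3), as do the time-to-event variables other than duration of response (Section 14.1.24). A trigger expressed as a multiple of median PFS naturally shares that origin. Starting at screening adds at most 21 days.
- Population: the FAS is primary for efficacy (Section 10.6.1) and the Safety Set for safety (Section 10.5). Both require at least one dose (Section 10.1).
- End-of-study date: SAP Table 8.2.1, footnote e, uses a patient-level end-of-study visit. If that date is missing, it takes the later of last follow-up visit and end of treatment. The protocol glossary describes stopping participation in a similar way.
- Actual observation: exposure (SAP Table 5), days in study (Listing 1.1), last contact (Listing 25), time from last tumour evaluation to end of study for censored patients (Table 8.2.1), and numbers at risk, events and censoring for PFS (Table 8.3.1).

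The end point of the clock and the treatment of closure remain open.

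**The case for a change.** The strongest case for a change is that Amendment 2 made this trigger its assurance of maturity, and an undefined trigger cannot be audited. In an open-label, single-arm study the sponsor sees the data as they accrue, so a loosely defined cut-off could be set afterwards. One sentence in Section 10.2 and one footnote in Table 1.3 would close the point.

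Part of this stands. The supplied pages do not fix the cut-off, and Table 1.3 is not linked to it. It cannot be said that Table 1.3 measures something different, because the trigger itself is undefined.

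The consequence is limited. A closed country supplies little more under either reading: the 30-day safety follow-up and the final progression update in Section 4.2. The choice therefore mainly decides how much longer open countries are observed. Kaplan-Meier estimates use whatever follow-up exists, and Table 8.3.1 shows how much there is. Potential follow-up to cut-off, a fixed calendar date and a reverse Kaplan-Meier median are all acceptable conventions, and choosing among them in advance would correct no planned result. The supplied SAP also consists of table, figure and listing shells, and Section 14.1.28 allows study-specific rules to sit in the reporting and analysis plan documentation, so a definition may exist in text not supplied.

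**Conclusion.** No change follows. This is missing detail that analysts would fill sensibly, most simply by counting from first dose to data cut-off in the FAS, and no stated rule gives a wrong answer. The 15-month figure is consistent with its justification (13.86 to 15.64 months). With N of about 244, the reading matters by under one month if a quarter of patients are in countries closed at the end of 2014, and by about 2 to 8 months at 50% to 75%. At 90% the closure-based reading would almost never reach 15 months, which is itself a reason to expect the common-cut-off reading.

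These sizes rest on linear accrual between the two documented counts, an assumed first-patient date, a single closure date and assumed closure shares. Amendment 2 speaks of a majority of countries, not of patients. Stating the convention used and the actual cut-off date in the study report would be good practice, but the plan can stand as written.
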